**Table 11: Management Guidelines for Immune-Related Adverse Events (Continued)**

Severity (CTCAE v5 Grade)	INCB099280	Evaluation and Management
Nephritis or renal dysfunction (creatinine increased)		
Grade 1 ( $> \text{ULN}$ to $1.5 \times \text{ULN}$ )	Consider temporarily holding INCB099280. If creatinine was within normal range at baseline and increased to Grade 1, recheck laboratory values in 48-72 hours.	Evaluate for alternative etiologies (eg, IV contrast, fluid status).
Grade 2 ( $> 1.5$ to $3.0 \times$ baseline; $> 1.5$ to $3.0 \times \text{ULN}$ )	
 
If creatinine was within the normal range at baseline, withhold INCB099280 until improvement to <math>\leq</math> Grade 1.
 
If creatinine was Grade 1 at baseline, INCB099280 may be continued and laboratory values checked in 48-72 hours. If creatinine is stable, INCB099280 may be continued and laboratory values rechecked in 48-72 hours. Additional consultation with the medical monitor is recommended. If creatinine increases, withhold INCB099280 and recheck chemistry laboratory values in 48 hours. INCB099280 treatment may resume when creatinine returns to Grade 1 or baseline.
 
	
 
Consultation with nephrology specialist advised.
 
Evaluate for alternative etiologies (eg, IV contrast, fluid status).
 
If other etiologies are ruled out, administer prednisone 0.5-1 mg/kg or equivalent with taper over at least 4 weeks once improved to <math>\leq</math> Grade 1.
 

Grade 3 ( $> 3.0 \times$ baseline; $> 3.0$ to $6.0 \times \text{ULN}$ ), Grade 4 ( $> 6.0 \times \text{ULN}$ ), or persistent Grade 2	Permanently discontinue if INCB099280 is directly implicated in the renal toxicity.	
 
Consultation with a nephrology specialist advised.
 
Evaluate for alternative etiologies (eg, IV contrast, fluid status).
 
Administer prednisone 1-2 mg/kg or equivalent with taper over at least 4 weeks.
 
If elevations persist for <math>> 3</math> days, consider additional immunosuppressive agents.
 

Diabetes mellitus		
Grade 1	Continue INCB099280 with close follow-up.	May initiate oral therapy for those with new-onset type 2 diabetes mellitus; intensify medical therapy for those with worsening type 2 diabetes mellitus.

**Table 11: Management Guidelines for Immune-Related Adverse Events (Continued)**

Severity (CTCAE v5 Grade)	INCB099280	Evaluation and Management
Diabetes mellitus (continued)		
Grade 2	May hold INCB099280 until glucose control is obtained.	
 
• Urgent consultation with an endocrine specialist and consultation for new-onset checkpoint inhibitor–associated diabetes mellitus.
 
• Insulin for checkpoint inhibitor–associated diabetes mellitus.
 
• Titrate therapy to achieve glucose control.
 

Grade 3 or Grade 4	Withhold INCB099280 until glucose control is achieved and $\leq$ Grade 1.	
 
• Admit for inpatient management of diabetic ketoacidosis, volume and electrolyte resuscitation, and insulin initiation.
 
• Consultation with an endocrine specialist for all participants.
 
• Insulin therapy for all participants.
 

Hypothyroidism		
Grade 1	Continue INCB099280.	Monitor TSH and FT4 as appropriate.
Grade 2	May continue or withhold until improved to $\leq$ Grade 1.	
 
• Consider consultation with an endocrinology specialist.
 
• Thyroid hormone replacement for symptomatic participants with any TSH elevation or participants with asymptomatic TSH levels persistently <math>> 10</math> mIU/L (measured 4 weeks apart).
 
• Monitor TSH and FT4 while titrating hormone replacement and once adequately resolved.
 

Grade 3 or Grade 4	Withhold INCB099280 until improvement to $\leq$ Grade 1 with appropriate thyroid hormone supplementation.	
 
• Consultation with an endocrinology specialist advised.
 
• Hospital admission for developing myxedema.
 
• Thyroid hormone replacement as in Grade 2.
 

Hyperthyroidism		
Grade 1	Continue INCB099280.	
 
• Monitor TSH and FT4 every 2-3 weeks.
 
• Beta-blocker for symptomatic relief.
 
• Consider consultation with an endocrine specialist for persistent hyperthyroidism.
 

Grade 2	Consider withholding until improvement to $\leq$ Grade 1.	
 
• Consider consultation with an endocrinology specialist.
 
• Beta-blocker for symptomatic relief.
 
• Hydration and supportive care.
 
• Consider consultation with an endocrine specialist for persistent hyperthyroidism.
 

Grade 3 or Grade 4	Withhold INCB099280 until improvement to $\leq$ Grade 1 with appropriate therapy.	
 
• Consultation with an endocrinology specialist advised.
 
• Prednisone 1-2 mg/kg or equivalent with taper.
 
• Beta-blocker for symptomatic relief.
 
• Consider thionamide.
 

**Table 11: Management Guidelines for Immune-Related Adverse Events (Continued)**

Severity (CTCAE v5 Grade)	INCB099280	Evaluation and Management
Hypophysitis or adrenal insufficiency		
Grade 1 or Grade 2	Consider withholding until improvement to $\leq$ Grade 1.	
Grade 1:
 
 
• Consultation with an endocrinology specialist advised.
 
• Systemic corticosteroid replacement with preference for hydrocortisone. Hormone replacement as clinically indicated.
 
 
Grade 2:
 
 
• Clinic evaluation to assess need for steroids and volume repletion.
 
• Hypophysitis: Consider oral pulse-dose therapy in participants with MRI findings of swelling or impending optic chiasm compression.
 
• Hormone supplementation as in Grade 1.
 

Grade 3 or Grade 4	Withhold INCB099280 until improvement to $\leq$ Grade 1.	
 
• Consultation with an endocrinology specialist advised.
 
• Inpatient management of fluids and stress-dose corticosteroids.
 
• Maintenance therapy as in Grade 1.
 

Myocarditis or pericarditis		
All grades		
 
• The prompt diagnosis of immune-mediated myocarditis is important, particularly in participants with baseline cardiopulmonary disease and reduced cardiac function.
 
• Immediately consult a cardiologist.
 
• Initial diagnostic workup should include a clinical evaluation, ECG, and telemetry monitoring as well as cardiac imaging, that is, echocardiogram and cardiac MRI (strongly recommended).
 
• Recommended laboratory testing includes cardiac biomarkers (creatinine kinase, brain natriuretic peptide, and troponin) and inflammatory biomarkers (erythrocyte sedimentation rate, C-reactive protein, and white blood cell count).
 
• Participants should be thoroughly evaluated to rule out any alternative etiologies (eg, disease progression, other medications, or infections via viral titers).
 
• Consider discussing with the study physician, as needed.
 
• Monitor symptoms daily. As some symptoms can overlap with lung toxicity, simultaneously evaluate for, and rule out, pulmonary toxicity as well as other causes (eg, pulmonary embolism, CHF, malignant pericardial effusions).
 

Elevated troponin Grade 1	Withhold treatment	
 
• Hold INCB099280. Recheck troponin 6 hours later. May consider resuming once normalized or if believed not to be related to INCB099280.
 

**Table 11: Management Guidelines for Immune-Related Adverse Events (Continued)**

Severity (CTCAE v5 Grade)	INCB099280	Evaluation and Management
Myocarditis or pericarditis (continued)		
Grade 2, Grade 3, and Grade 4 as well as biopsy-proven immune-mediated myocarditis, pericarditis (all grades)	Permanently discontinue INCB099280.	
 
Intensive care monitoring is strongly recommended.
 
Promptly start IV methylprednisolone (consider methylprednisolone pulse dosing [1 g/day for 3-5 days]); treat until cardiac function returns to baseline and then dose taper over 4-6 weeks.
 
If no improvement is noted within 24 hours on steroids, consider adding immunosuppressive agents (such as infliximab, antithymocyte globulin, and mycophenolate mofetil).
 
It is important to rule out sepsis and refer to the infliximab label for general guidance before using infliximab; infliximab is contraindicated in participants who have heart failure.
 

Nervous system disorders		
Grade 1	Continue INCB099280, or may withhold and monitor. Note: The following conditions require a hold of INCB099280: 
 
Aseptic meningitis
 
Encephalitis
 
	
 
Consultation with a neurology specialist is advised.
 
Monitor closely for any symptom progression.
 
Exclude alternative etiologies, empiric treatment as indicated.
 

Grade 2	Withhold INCB099280 until improvement to $\leq$ Grade 1. Note: Demyelinating diseases require INCB099280 to be stopped; may resume in consultation with neurology.	
 
Consultation with a neurology specialist advised and workup including MRI. Consider EMG, lumbar puncture, and CSF analysis.
 
Administer supportive care and corticosteroids.
 
Monitor closely for any symptom progression.
 
Workup for alternative etiologies, empiric treatment as indicated.
 

Grade 3	Withhold INCB099280 until improvement to $\leq$ Grade 1 OR Permanently discontinue INCB099280.	
 
Consultation with a neurology specialist advised and workup including MRI. Consider EMG, lumbar puncture, and CSF analysis.
 
Administer supportive care and corticosteroids.
 
Workup for alternative etiologies, empiric treatment as indicated.
 
Continuation, withholding, or discontinuation of INCB099280 will depend on the severity of the irAE and affected organ/organ system. Restarting participants after Grade 3 nervous system AEs requires medical monitor approval.
 

**Table 11: Management Guidelines for Immune-Related Adverse Events (Continued)**

Severity (CTCAE v5 Grade)	INCB099280	Evaluation and Management
Nervous system disorders (continued)		
Grade 4	Permanently discontinue INCB099280.	
 
• Consultation with a neurology specialist advised and workup including MRI. Consider EMG, lumbar puncture, and CSF analysis.
 
• Administer supportive care and/or corticosteroids.
 
• Workup for alternative etiologies, empiric treatment as indicated.
 

Other irAEs		
Grade 1	Continue INCB099280	
 
• Administer supportive care, which may include corticosteroids.
 
• Consider relevant specialist consultations, as appropriate.
 

Grade 2	Continue INCB099280 OR Withhold INCB099280 until improvement to $\leq$ Grade 1 OR Permanently discontinue INCB099280.	
Grade 3 or intolerable/ persistent Grade 2	Withhold INCB099280 until improvement to $\leq$ Grade 1 OR Permanently discontinue INCB099280.	
Grade 4 or recurrent Grade 3	Permanently discontinue INCB099280.	

#### 6.6.6. Dose-Modification Guidelines for Adverse Events Potentially Associated With Axitinib Treatment

Participants should be monitored throughout the study for the development of safety events known to be associated with axitinib treatment.

General guidance on specific safety events described with the use of axitinib is as follows:

- BP should be well controlled prior to initiating study treatment.
  - The median time to onset of hypertension (SBP > 150 mm Hg or DBP > 100 mm Hg) is within the first month of the start of treatment, but BP increases have been observed as early as 4 days after starting axitinib. See Section 6.6.6.1 for further details.
- Participants should be monitored for signs or symptoms of heart failure.
  - Underlying cardiac contractile dysfunction can either be left ventricular systolic dysfunction or left ventricular diastolic dysfunction (impaired relaxation, as is frequently seen in participants with arterial hypertension). See Section 6.6.6.2 for further details.

- Axitinib should be used with caution in participants who are at risk for or who have a history of arterial and venous embolic and thrombotic events.
  - Increases in hemoglobin or hematocrit (polycythemia) may occur during treatment with axitinib; an increase in red blood cell mass may increase the risk of embolic and thrombotic events.
- Palmar-plantar erythrodysesthesia syndrome (hand-foot syndrome) is a common skin reaction that should be anticipated (see Section 2.3).
  - Awareness and early recognition are important to ensure timely treatment and avoidance of dose reductions or treatment discontinuation.
  - It may have a serious impact on a participant's quality of life and, as a result, their ability to continue or complete study treatment.
  - Effective measures for the prevention and treatment (including systemic and topical treatments, axitinib dose reductions) exist; these approaches may allow participants to continue study treatment while reducing negative impacts on their quality of life.
  - A referral to a dermatologist is recommended.
- Liver-related adverse reactions:
  - The most commonly reported liver-related adverse reactions include increases in ALT, AST, and blood bilirubin.
  - Differentiating whether elevations in transaminase levels are attributable to INCB099280 or axitinib, or both, may be challenging, as no specific clinical picture or laboratory markers are available.
  - A referral to a hepatologist is recommended.
  - See Section 6.6.6.3 for further details.
- GI perforation and fistula formation:
  - Prior radiation therapy has been identified as a possible predisposing risk factor for fistula formation in participants undergoing treatment with axitinib.
  - Monitor participants for signs and symptoms of perforation and fistula.
- Reversible posterior leukoencephalopathy syndrome, also known as posterior reversible encephalopathy syndrome:
  - Should be considered in any participant presenting with headache, seizure, lethargy, confusion, blindness, and other visual and neurological disturbances.
  - It has been observed in association with mild to severe hypertension.
  - MRI is necessary to confirm the diagnosis.

Guidance on the management of specific safety events potentially associated with axitinib treatment is provided in Table 12, Table 13, and Table 14.

#### 6.6.6.1. Blood Pressure Measurement and Hypertension

Blood pressure will be monitored for the development or worsening of pre-existing hypertension at the timepoints indicated in [Table 3](#). Additionally, participants may be encouraged to monitor their BP at home as needed. Participants should be instructed to contact the site for guidance if BP measurements are > 150 mm Hg systolic and/or 100 mm Hg diastolic or if they develop signs or symptoms thought to be related to increased BP (eg, headache, visual disturbance).

The ESC/ESH and ACC/AHA place strong emphasis on accurate measurement of BP by using validated devices and multiple readings for the diagnosis and management of hypertension ([Whelton et al 2018](#), [Williams et al 2018](#)). Additionally, standardized clinical settings for a valid measurement include the following:

- Conditions:
  - Avoid smoking, caffeine, and exercise for 30 minutes; empty bladder; seated comfortably in a quiet environment for 5 minutes before beginning BP measurements.
  - Neither participant nor staff should talk before, during, and between measurements.
- Position:
  - Arm resting on table with midarm at heart level; back supported on chair, legs uncrossed and feet flat on floor.
- Cuff:
  - The cuff should be positioned at the level of the heart, with the back of the arm supported to avoid muscle contraction and isometric exercise-dependent increase in BP.
- Protocol:
  - Measure BP in both arms at first visit to detect possible between-arm differences. Use the arm with the higher value as the reference.
  - The ESC/ESH recommends repeated readings (3 BP measurements should be recorded 1-2 minutes apart, with additional measurements only if the first 2 readings differ by > 10 mm Hg or BP is unstable because of an arrhythmia).
  - BP is recorded as the average of the last 2 BP readings.

Hypertension should be managed in accordance with the ESC/ESH or ACC/AHA guidelines. Both guidelines have similar core strategies and recommend the use of agents from 4 drug classes (diuretics, CCBs, ACE inhibitors, or ARBs) where there is no compelling indication for selection of a specific BP-lowering medication. Additionally, both guidelines also advise combination therapy (usually an initial combination of ACE inhibitors or an ARB, a diuretic, and/or a CCB followed by a 3-drug combination if necessary) if there is no compelling indication for drug choice. However, treatment intensity and the choice of drugs should be based on clinical judgment (especially in participants with a high burden of comorbidity), participant preference, and team-based approach to assessing risk/benefit.

- General guidance:
  - The target SBP is  $\leq 140$  mm Hg and DBP  $\leq 90$  mm Hg, provided that the treatment is well tolerated.
  - Initiate antihypertensive drug therapy when SBP  $\geq 140$  mm Hg or DBP  $\geq 90$  mm Hg.
  - A referral to a cardiologist is recommended for participants who develop hypertension during the study, and management of hypertension should ideally be supervised by a cardiologist.
  - The plasma half-life of axitinib is 2 to 6 hours, and BP usually decreases within 1 to 2 days following dose interruption. Therefore, if axitinib is interrupted in participants receiving antihypertensive medication, monitor them closely for orthostatic hypotension (a reduction in SBP  $\geq 20$  mm Hg or in DBP  $\geq 10$  mm Hg within 3 minutes of standing).
- Guidance on the management of hypertension, based on severity, is provided in [Table 12](#).

#### **6.6.6.2. Left Ventricular Function and Heart Failure**

Left ventricular systolic and diastolic function will be monitored at the timepoints indicated in [Table 3](#). Since numerous echocardiographic techniques are used in the assessment of left ventricular function, sites should use their preferred method of assessment and supplement it by any other technique deemed essential to guide management. Every effort should be made to schedule serial monitoring at the same cardiac imaging facility.

Management of cardiovascular risk factors should be optimized prior to initiation of treatment with axitinib. Signs and symptoms of cardiac failure should be monitored throughout the study. Participants must be permanently discontinued from study drug for clinically manifested CHF. See [Table 12](#) for guidance on the management of cardiac failure and [Appendix D](#) for NYHA functional classifications of heart failure.

#### **6.6.6.3. ALT and AST Elevation**

General considerations when evaluating elevated transaminase levels are as follows:

- The determination of immune-related hepatitis mostly relies on the exclusion of other causes, including treatment with axitinib; however, the attribution of AST/ALT elevation to treatment with either INCB099280 or axitinib may be challenging. Potential alternative causes that should also be evaluated and excluded before more definitively concluding the attribution to study treatment include the following:
  - Exposure to other drugs, including over-the-counter and herbal medications that are potentially associated with DILI (eg, statins, acetaminophen)
  - History of alcohol use and recent alcohol use
  - Viral hepatitis A, B, C, and E; cytomegalovirus, Epstein-Barr virus, and other systemic infections

- Autoimmune screening tests
- Liver metastasis and obstructive hepatic disease
- Cardiac or vascular etiology (eg, any cause of severe hypoperfusion of the liver, severe cardiac failure)
- Other causes as appropriate
- Time to onset:
  - Early onset (compared to ICI-related elevations in transaminase levels that occur predominately with the first 6-12 weeks after treatment initiation) suggests the event is likely associated with axitinib after excluding other alternative explanations.
- Response to drug dechallenge:
  - A prompt recovery from elevation in transaminase levels in response to axitinib interruption without confounding by corticosteroid treatment suggests the event is likely associated with axitinib (after excluding other alternative explanations).
  - If the initial elevation in transaminase levels does not respond rapidly to axitinib interruption but responds to subsequent corticosteroid treatment, it suggests a potential for immune-mediated hepatitis by INCB099280. It should be kept in mind that not all cases of immune-mediated hepatitis will respond to corticosteroid treatment.
- A positive rechallenge (see notes below and further details in [Table 14](#); ie, recurrence of elevation in transaminase levels following resumption with study treatment) will provide further support for its attribution.
- Guidelines on causality elevation and management of AST/ALT elevations during axitinib/INCB099280 treatment are described (see [Table 14](#)) for action taken with study medication:
  - Promptly interrupt (or permanently discontinue) both study drugs and any other suspected concomitant medications, including over-the-counter and herbal medications and supplements.
  - Adequately monitor liver enzymes and LFTs. This should include AST, ALT, alkaline phosphatase, total bilirubin, direct bilirubin, and PT/INR. Repeat LFTs within 24 to 72 hours to confirm the initial laboratory value. Continue to monitor LFTs at least twice weekly, while evaluating other causes, until AST/ALT values are trending downward.

While corticosteroid therapy is essential for managing immune-mediated hepatitis, administering immunosuppressants prior to identifying the most likely causes of transaminase elevation will confound the causality assessment and impact proper management of the event. Initiating corticosteroids should be considered if transaminase elevation:

- Is associated with clinical significant hepatic dysfunction (eg, AST/ALT  $> 3 \times$  ULN with concurrent total bilirubin  $\geq 2 \times$  ULN (excluding biliary obstruction) and/or PT/INR  $\geq 1.5 \times$  ULN
- OR
- Has been persistent or further increased (without an alternative cause identified); consider observing liver biochemistry for approximately 3 to 7 days prior to making the decision if the participant is stable.

Rechallenge after AST/ALT elevation:

- Rechallenge should occur at the discretion of the investigator in consultation with the medical monitor. The guidelines in [Table 14](#) are suggestions; clinical judgment should always be used when deciding whether or not to restart each study drug.

Recommended axitinib dose modifications in case of drug-related toxicity are shown in [Table 12](#), [Table 13](#), and [Table 14](#).

**Table 12: Axitinib Toxicity Management Guidelines**

Event/Severity (CTCAE v5 Grade)	Management Guideline
Hypertension	
SBP $> 150$ mm Hg OR DBP $> 100$ mm Hg	
 
• SBP <math>< 150</math> mm Hg 
 
– Continue axitinib at the current dose level.
 
– Initiate/optimize antihypertensive therapy to achieve target SBP <math>\leq 140</math> mm Hg.
 
 
 
• SBP <math>> 150</math> mm Hg or DBP <math>> 100</math> mm Hg 
 
– Initiate/optimize antihypertensive therapy.
 
– Reduce axitinib dose by 1 dose level (see Table 9).
 
 
 

SBP $> 160$ mm Hg OR DBP $> 105$ mm Hg	
 
• Interrupt axitinib until BP <math>< 150/100</math> mm Hg.
 
• Initiate/optimize antihypertensive therapy (unless already on maximal antihypertensive therapy).
 
• Resume axitinib with a dose reduction of 1 level (see Table 9).
 

Grade 4 Life-threatening consequences (eg, malignant hypertension, transient or permanent neurologic deficit, hypertensive crisis)	Discontinue axitinib.

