**Table 9: Axitinib Dose-Reduction Scheme**

Initially Assigned Axitinib Dose	First Dose Reduction	Second Dose Reduction
5 mg BID	3 mg BID	2 mg BID
3 mg BID	2 mg BID	NA

Intraparticipant dose escalation is not permitted.

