### 6.6.7. Criteria for Permanent Discontinuation of Study Drugs Due to Unacceptable Toxicity

Unacceptable toxicity or the inability to tolerate study treatment with both INCB099280 and axitinib will require discontinuation of study treatment.

On a case-by-case basis, following discussion between the medical monitor and investigator, participants who are required to discontinue treatment with axitinib may continue treatment with INCB099280 until such time that an INCB099280 discontinuation criterion is met.

Study treatment must be permanently discontinued for the following:

- Any AE meeting a criterion for treatment discontinuation of INCB099280 and axitinib as detailed in [Table 11](#), [Table 12](#), [Table 13](#), and [Table 14](#).
- AEs requiring more than the allowed dose reductions of axitinib as detailed in [Table 9](#).
- A persistent AE requiring an interruption of study treatment for more than 3 weeks (21 days) unless a greater delay has been approved by the sponsor.
- The occurrence of an AE that is related to study drug that, in the judgment of the investigator or the sponsor's medical monitor, compromises the participant's ability to continue study-specific procedures or is considered to not be in the participant's best interest.

See Section [7](#) for discontinuation procedures.

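### Table 12 gives two opposite axitinib instructions, continue and reduce, for diastolic pressure above 100 and up to 105 mm Hg with systolic pressure below 150 mm Hg

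*Protocol*

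**What the plan says.** The hypertension block of Table 12 (protocol, Section 6.6.6) has three rows. The first is entered at "SBP $> 150$ mm Hg OR DBP $> 100$ mm Hg" and holds two bullets:

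- SBP below 150: "Continue axitinib at the current dose level", with antihypertensive treatment aimed at SBP of 140 or less.
- SBP above 150 or DBP above 100: start or optimise antihypertensives and "Reduce axitinib dose by 1 dose level".

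The second row is entered at "SBP $> 160$ mm Hg OR DBP $> 105$ mm Hg". Its instruction begins "Interrupt axitinib until BP" and continues with the limit 150/100 mm Hg; axitinib then resumes one level lower. The third row, for Grade 4 events, requires discontinuation.

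Other relevant text:

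- Table 9 sets the steps 5, 3 and 2 mg BID and adds "Intraparticipant dose escalation is not permitted".
- Section 6.6.7 lists "AEs requiring more than the allowed dose reductions of axitinib" among the reasons for permanent discontinuation.
- Section 6.6.6.1 covers blood pressure measurement and when to treat ("Initiate antihypertensive drug therapy when SBP" is at least 140, or DBP at least 90). It refers to Table 12 for management by severity.

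**The concern.** The condition of the second bullet is the same as the entry condition of the row, so the reduction applies to everyone in the row. The first bullet then tells sites to leave the dose alone for some of the same people. It sets no limit on DBP and reads like a lower severity tier placed in the wrong row.

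Hypertension is among the leading axitinib toxicities in the protocol's own background data: 40% any grade and 16% Grade 3 or 4 as monotherapy (Section 2.3.1), and 44.5% and 22.1% with pembrolizumab (Section 2.3.2). Sites will therefore use this block, although the share of readings in the disputed band is unknown.

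Two things are at stake:

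- **The participant's dose.** Because re-escalation is barred, a reduction is permanent.
- **An endpoint.** Adverse events leading to interruption, reduction or discontinuation are a primary endpoint in Part 1 and a secondary endpoint in Part 2 (Table 4). Two sites that both follow the protocol could record different outcomes for the same blood pressure.

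In Part 1 there is a possible further effect. Section 6.5 ties DLT evaluability to 32 doses at the assigned level, which is 32 / 2 = 16 days of BID dosing. An early reduction could therefore affect whether a participant without a DLT counts as evaluable.

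**Working it through.** The protocol states no figure to reproduce; this is a check of logic.

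**Inputs, all from Table 12**

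| Element | Condition (mm Hg) | Axitinib action |
|---|---|---|
| Row 1 entry | SBP > 150 or DBP > 100 | see bullets |
| Row 1, bullet 1 | SBP < 150 | unchanged |
| Row 1, bullet 2 | SBP > 150 or DBP > 100 | down one level |
| Row 2 entry | SBP > 160 or DBP > 105 | interrupt, resume one level lower |

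**Step 1: can bullet 1 apply on its own?** Being in row 1 with SBP < 150 rules out the systolic route, so DBP > 100. That satisfies bullet 2. No reading in the row therefore meets bullet 1 without also meeting bullet 2.

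**Step 2: where is the conflict?** It requires SBP < 150 and DBP > 100. Row 2 takes over at DBP > 105. What remains is SBP < 150 with DBP > 100 up to 105, or DBP 101 to 105 in whole mm Hg.

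**Step 3: enumeration as a cross-check.** All whole-number pairs with SBP 110 to 180 and DBP 60 to 120 were tested. Of these, 665 fall in row 1 and not in row 2:

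- Both bullets met: SBP 110 to 149 (40 values) × DBP 101 to 105 (5 values) = 200.
- Reduce only: 5 (SBP 150, DBP 101 to 105) + 10 × 46 (SBP 151 to 160, DBP 60 to 105) = 465.
- Continue only: 0.

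The totals depend on the grid chosen and are not patient frequencies. Only the zero matters, and it holds on any grid.

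**Step 4: how far apart are the two instructions?** Using the steps in Table 9:

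- From 5 mg BID: 10 against 6 mg/day, (10 − 6) / 10 = 40% lower.
- From 3 mg BID: 6 against 4 mg/day, (6 − 4) / 6 = 33% lower.
- From 2 mg BID: no lower level exists, so reducing means discontinuing axitinib under Section 6.6.7, with INCB099280 alone only case by case.

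**Step 5: does any other text settle it?**

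- The rule in Section 6.6 to choose the most conservative management concerns doubt about which of the two drugs caused an event. It does not address two instructions for one drug.
- Section 6.6.6.1 gives no axitinib dose rule of its own and refers back to Table 12.
- Section 6.6.3 says to follow the guidelines and clinical judgment, without ranking the bullets.

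**The case against.** The strongest reply concerns weight, since the overlap itself is plain on the page.

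- **Intent can be guessed.** Bullet 1 is purely systolic in both condition and target, whereas bullet 2 names DBP. A reader with DBP 103 would probably reduce, which fits the gradient to the interrupt row. This is a reasonable inference, but the protocol does not state it.
- **These are guidelines.** Section 6.6.2 makes reductions depend on individual tolerability, Section 6.6.3 allows clinical judgment and asks for sponsor contact on safety concerns, and Section 6.6.6.1 recommends cardiology referral. Either action could be defended. Yet where the table intends a choice it says so: Grade 3 hyperthyroidism explicitly offers the same dose or one level lower at the investigator's discretion. The hypertension row offers no such choice.
- **Safety is bounded.** Both bullets call for antihypertensive treatment, and the rules above SBP 160 or DBP 105 are clear. This stands.
- **The 2 mg BID case is rare.** It needs two earlier reductions from 5 mg BID, or one from 3 mg BID, and then a reading in the narrow band. This also stands; it is an edge case.
- **The statistical effect is probably small.** The endpoint pools all toxicities and is summarised descriptively, with no formal tests. Sample size, the futility rule and the response analysis are untouched. This stands too, and it limits the importance of the point without removing the contradiction.

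**Conclusion.** The contradiction is real as printed. For SBP below 150 with DBP above 100 and up to 105 mm Hg, Table 12 tells sites both to keep the axitinib dose and to lower it, and no other text decides between them. Within its row the continue instruction never applies alone.

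The scope is a 5 mm Hg diastolic band. The instructions differ by 40% or 33% of the daily dose, or by continuing against stopping at 2 mg BID. Modifications for SBP above 150, DBP above 105 or other toxicities are unaffected. How many participants would fall in the band cannot be derived from the protocol.

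The conclusion rests only on the row conditions as they stand and on reading the second row as taking precedence above its thresholds. It merits correction because a wrong reduction is irreversible and is counted in the dose-modification endpoint.

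**What to change.** Replace the present first row with two tiers that do not overlap:

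- **Lower tier:** SBP 140 to 150 and/or DBP 90 to 100, with neither SBP above 150 nor DBP above 100. Keep axitinib unchanged and start or optimise antihypertensives. This matches the 140/90 treatment threshold in Section 6.6.6.1.
- **Middle tier:** SBP above 150 to 160 or DBP above 100 to 105. Start or optimise antihypertensives and reduce axitinib by one level.

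Leave the interrupt row (SBP above 160 or DBP above 105) and the Grade 4 row as they are.

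If the sponsor instead means to continue the dose when only DBP is raised to between 100 and 105, delete the diastolic condition from the reduce bullet. In that case also change the continue bullet to SBP of 150 or less; otherwise a reading of exactly 150 with DBP above 100 would meet neither bullet.

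Either version costs only table wording at the next amendment and a memo to sites. No change to sample size or analysis is needed.
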